6.4. Investigational Product Administration

The participants will be instructed to self-insert the Dapivirine Vaginal Ring-004 at the Enrolment Visit, and monthly thereafter. The participants will be reminded of proper vaginal ring insertion and removal procedures.

During the 3-monthly trial visit schedule, participants will be instructed to remove the vaginal rings and self-insert each of the two additional rings at monthly intervals until their next scheduled research centre visit. The self-insertion and removal of the rings should take place at the research centres during the months that the participants attend their scheduled trial visits. Participants should be advised to continue ring use through menses.

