^e Used a condom ^f Had anal sex since last visit ^g Had a menstrual bleeding/spotting since last visit ^h Had ring expelled/removed since last visit

ⁱ Cleaned ring before reinsertion ^j Inserted fingers into vagina

Table 14.6.8
 Participant Questionnaire – 3 Month Follow-Up
 Safety Population

Trial Month X	Statistic	IPM 032 Overall (N=XXX)
View on the information sheet		
The sheet is good as it is	n (%) ^a	X (X.X)
The sheet is hard to understand	n (%) ^a	X (X.X)
The sheet needs more information	n (%) ^a	X (X.X)
The sheet needs to be changed	n (%) ^a	X (X.X)
Did not read the instruction sheet	n (%) ^a	X (X.X)
Can't remember (the instruction sheet)	n (%) ^a	X (X.X)
Since your last scheduled visit, was it easy or difficult to remove your ring?		
Easy to remove	n (%) ^h	X (X.X)
Difficult to remove	n (%) ^h	X (X.X)
Sometimes easy, sometimes difficult to remove	n (%) ^h	X (X.X)
Neither easy nor difficult to remove	n (%) ^h	X (X.X)
N/A, I did not remove my own ring	n (%) ^h	X (X.X)
Since your last scheduled visit, was it easy or difficult to insert a new ring?		
Easy to insert	n (%) ^h	X (X.X)
Difficult to insert	n (%) ^h	X (X.X)
Sometimes easy, sometimes difficult to insert	n (%) ^h	X (X.X)
Neither easy nor difficult to insert	n (%) ^h	X (X.X)
N/A, I did not insert my own ring	n (%) ^h	X (X.X)

Programmers Notes:

- Please add in 'Chose not to answer' where applicable
- Please repeat the table for all available Trial Months

Percentages are calculated out of the number of participants ^a In the safety population ^b Left rings at the research centre ^c With main partner ^d Took rings

^e Used a condom ^f Had anal sex since last visit ^g Had a menstrual bleeding/spotting since last visit ^h Had ring expelled/removed since last visit

ⁱ Cleaned ring before reinsertion ^j Inserted fingers into vagina

Table 14.6.8
 Participant Questionnaire – 3 Month Follow-Up
 Safety Population

Trial Month X	Statistic	IPM 032 Overall (N=XXX)
Experience with the bag given to put the used rings in		
The bag was easy to open and close	n (%) ^a	X (X.X)
The bag was hard to open and close	n (%) ^a	X (X.X)
The bag was sometimes lost	n (%) ^a	X (X.X)
The bag was sometimes used for something else	n (%) ^a	X (X.X)
The bag was fine	n (%) ^a	X (X.X)
I did not like having to keep the empty bag(s)	n (%) ^a	X (X.X)
I did not like having the used ring(s) in the house	n (%) ^a	X (X.X)
I did not like carrying the used ring(s) to the research centre	n (%) ^a	X (X.X)

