Someone found the ring bag(s) (with or without rings),	n (%) ^a	X (X.X)
I did not like the look of the bag	n (%) ^a	X (X.X)
It was difficult to bring the bags back to the clinic	n (%) ^a	X (X.X)
Other	n (%) ^a	X (X.X)
Not applicable, I did not use the bags or return a ring since the last visit	n (%) ^a	X (X.X)
Place of storage of the unused ring(s) before insertion		
In bag/handbag	n (%) ^d	X (X.X)
In a shared cupboard/drawer in the house	n (%) ^d	X (X.X)
In a personal cupboard/drawer in my room/in the house	n (%) ^d	X (X.X)
In a locked place that no-one else could access	n (%) ^d	X (X.X)
At someone else's house	n (%) ^d	X (X.X)
Other	n (%) ^d	X (X.X)
Not applicable, I did not have any extra unused rings since the last visit	n (%) ^d	X (X.X)

Programmers Notes:

- Please add in 'Chose not to answer' where applicable
- Please repeat the table for all available Trial Months

Percentages are calculated out of the number of participants ^a In the safety population ^b Left rings at the research centre ^c With main partner ^d Took rings

^e Used a condom ^f Had anal sex since last visit ^g Had a menstrual bleeding/spotting since last visit ^h Had ring expelled/removed since last visit

ⁱ Cleaned ring before reinserion ^j Inserted fingers into vagina

Table 14.6.8
 Participant Questionnaire – 3 Month Follow-Up
 Safety Population

Trial Month X	Statistic	IPM 032 Overall (N=XXX)
Experience when storing the unused ring(s)		
There were no problems storing the unused ring(s)	n (%) ^d	X (X.X)
I was concerned that someone might find the unused ring	n (%) ^d	X (X.X)
I sometimes forgot where I had stored the unused ring(s)/lost the unused ring(s)	n (%) ^d	X (X.X)
The ring(s) accidentally got thrown away	n (%) ^d	X (X.X)
I did not like storing the unused rings	n (%) ^d	X (X.X)
Someone found the ring(s) and that was problematic	n (%) ^d	X (X.X)
Someone found the ring(s) but it was not problematic	n (%) ^d	X (X.X)
Other	n (%) ^d	X (X.X)
Not applicable, I did not have any extra unused rings since the last visit	n (%) ^d	X (X.X)
Place of storage of the used ring(s) after removal		
I returned the used ring(s) to the research centre straight away	n (%) ^h	X (X.X)
In a bag/handbag	n (%) ^h	X (X.X)
In a shared cupboard/drawer in the house	n (%) ^h	X (X.X)
In a personal cupboard/drawer in my room/in the house	n (%) ^h	X (X.X)
In a locked place that no-one else could access	n (%) ^h	X (X.X)
At someone else's house	n (%) ^h	X (X.X)
Other	n (%) ^h	X (X.X)

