My neighbors, family, or friends (as above) are happy about my participation in this study (if they are aware of participation)	n (%) ^a	X (X.X)
Other	n (%) ^a	X (X.X)
Preference if not in the DREAM study: Prefer to come to the health care clinic/provider for new rings each month or every three months		
Each month	n (%) ^a	X (X.X)
Every three months	n (%) ^a	X (X.X)
Don't mind	n (%) ^a	X (X.X)
Depends	n (%) ^a	X (X.X)

Programmers Notes:

- Please add in 'Chose not to answer' where applicable
- Please repeat the table for all available Trial Months

Percentages are calculated out of the number of participants ^a In the safety population ^b Who left their rings at the research centre ^c With main partner ^d Who took their rings

^e Who used a condom ^f Who had anal sex since last visit ^g Who had a menstrual bleeding/spotting since last visit ^h Who had ring expelled/removed since last visit

ⁱ Who cleaned ring before reinsertion ^j Who inserted fingers into their vaginas

Table 14.6.8
 Participant Questionnaire – 3 Month Follow-Up
 Safety Population

Trial Month X	Statistic	IPM 032 Overall (N=XXX)
Preference if not in the DREAM study: Prefer to come to the health care clinic/provider for HIV tests each month or every three months		
Each month	n (%) ^a	X (X.X)
Every three months	n (%) ^a	X (X.X)
Don't mind	n (%) ^a	X (X.X)
Depends	n (%) ^a	X (X.X)
Currently have a main sex partner		
Yes	n (%) ^a	X (X.X)
No	n (%) ^a	X (X.X)
Currently live with main partner		
Yes	n (%) ^b	X (X.X)
No	n (%) ^b	X (X.X)
Other partners since last scheduled visit		
0 - 1	n (%) ^a	X (X.X)
>= 2	n (%) ^a	X (X.X)
Number of sex acts over the past month	Mean (q1,med,q3) SD (Min, Max)	XX.X (XX.X,XX.X,XX.X) XX.XX (XX, XX)
Use of a male condom over the past month		
Always	n (%) ^a	X (X.X)
Sometimes	n (%) ^a	X (X.X)
Often	n (%) ^a	X (X.X)
Never	n (%) ^a	X (X.X)

Programmers Notes:

- Please add in 'Chose not to answer' where applicable
- Please repeat the table for all available Trial Months

Percentages are calculated out of the number of participants ^a In the safety population ^b Who left their rings at the research centre ^c With main partner ^d Who took their rings

^e Who used a condom ^f Who had anal sex since last visit ^g Who had a menstrual bleeding/spotting since last visit ^h Who had ring expelled/removed since last visit

ⁱ Who cleaned ring before reinsertion ^j Who inserted fingers into their vaginas

Table 14.6.8
 Participant Questionnaire – 3 Month Follow-Up

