Accidentally came out	n (%) ^h	X (X.X)
Other	n (%) ^h	X (X.X)
When the ring was removed/expelled did you clean the ring before reinsertion?		
Yes	n (%) ^h	X (X.X)
No	n (%) ^h	X (X.X)
Programmers Notes:		
- Please add in 'Chose not to answer' where applicable		
- Please repeat the table for all available Trial Months		

Percentages are calculated out of the number of participants ^a In the safety population ^b Left rings at the research centre ^c With main partner ^d Took rings

^e Used a condom ^f Had anal sex since last visit ^g Had a menstrual bleeding/spotting since last visit ^h Had ring expelled/removed since last visit

ⁱ Cleaned ring before reinsertion ^j Inserted fingers into vagina

Table 14.6.8
 Participant Questionnaire – 3 Month Follow-Up
 Safety Population

Trial Month X	Statistic	IPM 032 Overall (N=XXX)
What did you use to clean the ring when it was removed/expelled?		
Water only	n (%) ^j	X (X.X)
Soap only	n (%) ^j	X (X.X)
Water and soap	n (%) ^j	X (X.X)
Disinfectant		
Water and soap	n (%) ^j	X (X.X)
Disinfectant	n (%) ^j	X (X.X)
Herbal products	n (%) ^j	X (X.X)
Traditional medicine	n (%) ^j	X (X.X)
Bubble bath	n (%) ^j	X (X.X)
Bath salts	n (%) ^j	X (X.X)
Dishwashing liquid	n (%) ^j	X (X.X)
Other	n (%) ^j	X (X.X)
Inserted fingers into vagina since last schedule visit		
Yes	n (%) ^a	X (X.X)
No	n (%) ^a	X (X.X)
Reason for inserting fingers into vagina		
Check the position of the ring	n (%) ^j	X (X.X)
Insert/remove the ring	n (%) ^j	X (X.X)
Cleaning	n (%) ^j	X (X.X)
Sexual pleasure	n (%) ^j	X (X.X)
Insert a product for the management of menses	n (%) ^j	X (X.X)
Other	n (%) ^j	X (X.X)

Programmers Notes:

- Please add in 'Chose not to answer' where applicable
- Please repeat the table for all available Trial Months

Percentages are calculated out of the number of participants ^a In the safety population ^b Left rings at the research centre ^c With main partner ^d Took rings

^e Used a condom ^f Had anal sex since last visit ^g Had a menstrual bleeding/spotting since last visit ^h Had ring expelled/removed since last visit

ⁱ Cleaned ring before reinsertion ^j Inserted fingers into vagina

Table 14.6.9
 Participant Questionnaire – Last Product Use Visit
 Safety Population

Trial Month X	Statistic	IPM 032 Overall (N=XXX)
Decision on extra rings, during three monthly visits		
Always took them	n (%) ^a	X (X.X)
Always left them at the research centre to collect monthly	n (%) ^a	X (X.X)

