2	What are your reasons for leaving the rings at the research centre today?
3	Did you have an additional HIV test at the research centre when you returned to collect your ring (in-between the study visits)?
4	Does your main partner know you are in the study and wearing a vaginal ring?
5	The research centre staff showed you how to insert and remove your ring. You were also given an instruction sheet that explains this. Was the sheet helpful, or does it need to be changed?
6	Thinking back since your last visit, was it easy or difficult to remove your ring?
7	Thinking back since your last visit, when you inserted a new ring, was it easy or difficult?
8	You were given a bag(s) to put the used ring in when returning it to the research centre. Please describe your experiences with the bag(s)?
9	For those who took extra rings: Where did you store the unused ring(s) before insertion?
10	For those who took extra rings: You personally stored the unused rings before using them. What was it like storing the unused ring(s)?
11	For those who did not return the used ring to the research centre straight away: Where did you store the used ring(s) after removing it/them?
12	For those who did not return the used ring to the research centre straight away: You stored the used ring before bringing it back to the research centre for your next scheduled visit. What was it like storing the used ring(s)?
13	At each regularly scheduled visit, you gave a sample of blood and vaginal fluids. Please tell me what your preferences are.
14	Below is a list of things that some women may like about participating in this study (DREAM). Please order these, where 1 means you liked it the most, and 5 means you liked it the least.
15	I'm going to read a list of things that some women have experienced during other study/studies. Please tell me if you have experienced any of these things in this study (DREAM).
15a	Length of time spent at the research centre for the study visits was too long. If yes, specify how long.
15b	Length of time spent at the research centre to pick up rings was too long. If yes, specify how long.
15c	Transport to the research centre for scheduled visits was a problem. If yes, specify.
15d	I was treated well when coming to the research centre for regular visits.
15e	I was treated well when I came to the research centre to pick up rings.
15f	Transport to pick up rings was a problem (if applicable). If yes, specify.

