15g	If partner knows about participation (see question 4): My partner is happy about my participation in the study.
15h	My neighbors, family, or friends know about my participation in this study. If yes, specify if neighbor/friends/family.
15i	If neighbor, friends, or family knows about participation (see above): My neighbors, family, or friends (as above) are happy about my participation in this study
15j	Other
16	If you were not in a study, would you prefer to come to the health care clinic/provider for new rings each month, or every three months?
17	If you were not in a study, would you prefer to come to the health care clinic/provider for an HIV test each month, or every three months?
18	Do you currently have a main sex partner?
18a	How long has he been your partner?
19	Do you and your main partner currently live together?
20	Have you had any other partners since your last scheduled visit?

Listing 16.2.5.9
Participant Questionnaire – 3 Month Follow-Up
Safety Population

20a If yes, indicate number.

21 We need to know how often you usually have sex. Think about the past four weeks, which is about one month. Over the past four weeks, how many rounds of vaginal sex did you have?

22 In the past month, how frequently did you use a male condom during vaginal sex?

23 In the past month, how frequently did you use a female condom during vaginal sex?

24 During the last round of vaginal sex you had, did you use a condom?

25 Since your last scheduled visit, have you had anal sex?

26 How worried are you that you might get infected with HIV in the next year?

27 Since your last scheduled visit, have you had any menstrual bleeding or any menstrual spotting?

28 Since your last scheduled visit, what have you used to control or manage the menstrual blood or spotting? Mark all that apply, using numbers for only those that apply - with 1 for the item used most, 2 for next most frequent, and so on until least frequent.

29 Since your last scheduled visit, has your ring been removed/expelled between scheduled removal dates?

30 What was the reason the ring was removed/expelled at this time?

31 When the ring was removed/expelled did you clean the ring before reinsertion?

32 What did you use to clean the ring when it was removed or expelled?

33 Since your last scheduled visit have you inserted your fingers into your vagina for any reason?

34 What was the reason for inserting your fingers into your vagina?

Listing 16.2.5.9

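### Several rows of questionnaire Tables 14.6.7 and 14.6.8 are divided by a subgroup that does not match the item, so their percentages would be wrong or wrongly restricted

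*SAP*

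**What the plan says.** Each questionnaire shell in SAP Appendix 1 carries a footnote that defines lettered subgroups as percentage denominators.

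- **Table 14.6.8, letter h.** The footnote reads "Had ring expelled/removed since last visit". The letter is attached to both ease-of-use blocks, to the block headed "Place of storage of the used ring(s) after removal", and to the block on the experience of storing used rings. It is also attached to the reasons for removal or expulsion, where it fits.
- **The item behind h.** Question 29 in Listing 16.2.5.9 asks: "Since your last scheduled visit, has your ring been removed/expelled between scheduled removal dates".
- **Routing of the storage items.** Question 11 in the same listing begins: "For those who did not return the used ring to the research centre straight away: Where did you store the used ring(s) after removing it/them". Question 12 has the same routing.
- **Ring changes at home.** Protocol 6.4 says that in the 3-monthly phase "participants will be instructed to remove the vaginal rings and self-insert each of the two additional rings at monthly intervals".
- **Table 14.6.9 (last product use visit).** The ease-of-use and used-ring storage rows are divided by the safety population.
- **Table 14.6.8, letter b.** The rows on living with the main partner carry b, which the footnote on that page defines as "Who left their rings at the research centre". Letter c, women with a main partner, is defined in the same footnote.
- **Table 14.6.7, letter d.** Reasons for inserting fingers carry d, women with recent menstrual bleeding or spotting. Letter e, women who inserted fingers, is defined but not used for these rows.
- **Two uncertain places.** In Table 14.6.8 the answers to "What did you use to clean the ring when it was removed/expelled" carry j (inserted fingers) rather than i (cleaned the ring). On the second page of Table 14.6.6, b is defined as women who cleaned the ring; on the first and third pages it means women whose ring was expelled or removed.

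**The concern.** A programmer will treat the footnote letters as instructions. Where the letter names a group unrelated to the question, the percentage has no clear meaning. The shells do not say whether the numerator is limited to the denominator group, so two programmers could produce different wrong figures from the same shell.

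The rows concerned describe how women managed ring removal, insertion and storage at home. That is useful supporting information for 3-monthly dispensing. The same items are on a different base in Table 14.6.9, so a reader who sets the two tables side by side would be misled.

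**Working it through.** The shells are empty and the SAP states no percentage for these rows, so there is no figure of the plan's own to reproduce. The check has two parts.

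**1. Does the letter match the item?**

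| Rows | Base in shell | Group the item applies to |
|---|---|---|
| 14.6.8 ease of removal and insertion | h: ring expelled or removed | women who removed or inserted a ring, including scheduled home changes |
| 14.6.8 used-ring storage, two blocks | h | women who did not return the used ring at once (questions 11 and 12) |
| 14.6.8 living with main partner | b: left rings at centre | c: with main partner |
| 14.6.7 reasons for inserting fingers | d: menstrual bleeding | e: inserted fingers |
| 14.6.8 cleaning product | j: inserted fingers | i: cleaned ring (check) |
| 14.6.6 second page, ease rows | b: cleaned ring | neither meaning of b fits inserting a new ring (check) |

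Neighbouring rows show what was probably meant. In Table 14.6.8 the unused-ring storage rows use d, women who took rings, which follows the routing. Table 14.6.7 divides its own partner row by women with a main partner, also lettered b. In Table 14.6.9, j does mean women who cleaned the ring. The letters look carried over between tables.

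**2. What would the error do?**

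Let s be the share of all women giving an answer, r the share in the denominator subgroup, and e the share to whom the item applies. With unrestricted numerators:

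- percentage shown = 100 × s / r, which exceeds 100% when s > r;
- distortion relative to the right base = e / r.

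The trial documents give none of these shares. The nearest figure for r is 18% (22% with pharmacy records) of women with any removal or expulsion over the whole of IPM 011, an earlier placebo-ring trial (Protocol 1.4.3). It is used here only as one assumption among several. All other shares are assumed.

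Rows under h, percentage shown:

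| r | s = 40% | s = 60% |
|---|---|---|
| 18% | 222% | 333% |
| 22% | 182% | 273% |
| 50% | 80% | 120% |
| 80% | 50% | 75% |

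Rows under h, distortion e / r:

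| r | e = 50% | e = 80% | e = 95% |
|---|---|---|---|
| 18% | 2.8 | 4.4 | 5.3 |
| 22% | 2.3 | 3.6 | 4.3 |
| 50% | 1.0 | 1.6 | 1.9 |

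Other rows, as (right base) / (base used):

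- Living with main partner, 80–95% partnered and 5–30% leaving rings: from 0.80/0.30 = 2.7 to 0.95/0.05 = 19.
- Cleaning product, 10–18% cleaned and 30–60% inserted fingers: from 0.10/0.60 = 0.17 to 0.18/0.30 = 0.60, so too low.
- Reasons for inserting fingers, 20–90% inserted and 40–70% with bleeding: from 0.20/0.70 = 0.29 to 0.90/0.40 = 2.25, so either direction.

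If numerators are restricted to the subgroup, no single row exceeds 100%. The h rows then leave out every woman whose only ring changes were scheduled ones.

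**The case against.** The strongest reply is that these are descriptive shells with no test or decision attached, that counts stand beside the percentages, and that full listings are planned. That is true and limits the consequence, but a wrong denominator remains wrong.

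Second, footnote h taken literally could include scheduled home changes, which would shrink the error. The wording allows this. However, question 29 and the use of h for the removal-reason rows both point to unscheduled removal, and under either reading h is not the routing of questions 11 and 12.

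Third, two of the letters may be slips in the footnote or in text extraction. Superscript i and j are easily confused, and only one page of Table 14.6.6 differs from its neighbours. Part B question 5 in Listing 16.2.5.7 is also routed to women who removed their ring, so b in its usual meaning would suit the removal row, though not the insertion row. This stands, so both places are offered for checking.

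Fourth, answers summing to more than 100% prove nothing, because the listings allow multiple responses. That is correct; the test above is applied to single rows.

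Fifth, the 3-month items ask about the time since the last visit, while the last-visit storage items cover the whole study. A common denominator rule would remove one inconsistency but would not make the tables fully comparable. This stands.

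**Conclusion.** The denominators are wrong as written for the h rows and the partner rows in Table 14.6.8 and for the finger-reason rows in Table 14.6.7. The cleaning-product rows in Table 14.6.8 and the second page of Table 14.6.6 are probably wrong too, subject to checking the source file.

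A reader might infer that all these percentages would be several-fold too high. The documents do not support that. Large inflation arises only for the h and partner rows, only with unrestricted numerators, and only if the subgroup is small. The cleaning rows would tend to be too low, and the finger-reason rows could go either way. The 18–22% figure belongs to another trial and a different period.

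A reader might also infer that exploratory objective 1 is compromised. SAP 9.4.1 lists the feasibility items (questions 1, 2, 16 and 17 of the 3-month questionnaire, with their counterparts at other visits, and ring returns) and reports them in Table 14.6.1. None of the disputed rows is among them. No primary or secondary endpoint is touched.

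**What to change.** In the Appendix 1 shells:

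1. Table 14.6.8: replace h on the ease-of-use and used-ring storage rows with the women routed to each item who answered it at that visit, and change b to c for living with the main partner.
2. Table 14.6.7: change d to e for reasons for inserting fingers.
3. Check j against i for the cleaning product in Table 14.6.8, and footnote b on the second page of Table 14.6.6; correct them if confirmed. Give the insertion row in Table 14.6.6 its own base.
4. Apply the same routing rule to the matching rows of Table 14.6.9.
5. Add one sentence to the shells: every numerator is a subset of its denominator. State also whether not-applicable answers count in the denominator.

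The cost is a few footnote edits and matching program changes, with no new data. SAP Section 1 exempts only formatting changes to the appendices from signature approval. A change of denominator is more than formatting, so it should be documented.
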